9.2.2. Study Location

The study is planned to be performed in Germany enrolling MS patients registered in the PSP of the MSSC.

9.2.3. Overall Study Duration and Follow-Up

9.2.3.1. Enrollment

The study period will start with the identification and enrollment of patients meeting the eligibility criteria. Recruitment is planned for 3 months. The end of study is defined as end of overall data collection when the database for analysis is completely available.

The Sponsor may terminate or prolong this study at any time, after informing the participating parties.

Data of the retrospective study part will be extracted from the German MS Service-Center database on the basis of the PSP registration form, i.e. the signed privacy policy. No separate patient information and consent procedure is planned for this part.

The study participation in the prospective study part starts with signature of the ICF and ends with the completion of the patient questionnaire. As the provision of the ICF by the MSSC and the return of the signed ICF by the patient is done by mail, both actions are expected to take 1-2 weeks. The telephone interview will take place only after having obtained the signed ICF. Depending on the availability of the patient for the telephone interview, another week has to be calculated resulting in an average study duration of about 2-3 weeks per patient in the prospective study part.

Patients in the prospective study part are informed that they have the right to withdraw from the study at any time, without prejudice to their medical care, and that they are not obliged to state their reasons. Any withdrawal must be fully documented in the MSSC data base. Withdrawn patients are not followed-up.

Unique identification numbers will be assigned to all pregnancy reports of participants enrolled in the study to track them throughout the study. In case of multiple pregnancies, separate identification numbers will be assigned for the pregnancies. Any identification

CONFIDENTIAL

The information contained herein may not be used, disclosed, or published without the written consent of Biogen MA Inc.

numbers that are assigned will not be reused even if a participant withdraws from the study prematurely.

An individual study participant may be included only once in the study – however, data of multiple pregnancies will be collected separately.

Participants who prematurely withdraw from the study for any reason will not be eligible to re-enroll.

9.2.3.2. Withdrawal of Participants from the Study

Participants in the prospective study part may withdraw consent to be in the study at any time. If withdrawal occurs before the telephone interview, the MSSC will collect no further information. Consent withdrawal of the prospective part of the study will be documented in the MSSC database.

9.2.3.3. Lost to Follow-Up

If a participant could not be contacted by the MSSC following the provision of the signed ICF, the MSSC may consider a participant lost to follow up after 5 failed documented telephone contacts and one failed email contact attempt. In this case, the questionnaire will not be filled in. If the MSSC ascertains a participant has died, the death should be recorded and reported within postmarketing channels as described in Section 11.3.1.1.

9.3. Variables

Information collected for analysis is outlined in Section 16.

9.4. Data Sources

9.4.1. Retrospective Data Capture

Main data source for the retrospective data capture is the MSSC database, i.e. the entered pregnancy report (to be completed as soon as pregnancy becomes known) and pregnancy outcomes report (to be completed after completion of pregnancy).

The following data is extracted from the MSSC database:

- Demographic data (age, height, weight)
- SC Peginterferon beta-1a or IM Interferon beta-1a use, including treatment duration, prior to, during and after pregnancy
- Concomitant medication prior to and during pregnancy
- Pregnancy outcome (live birth without defect, live birth with defects, ectopic pregnancy, spontaneous abortion, elective termination of pregnancy, preterm birth, stillbirth), including gestation week and description of abnormalities of the fetus, reason for termination, diagnostics, etc.
- Complications during pregnancy

CONFIDENTIAL

The information contained herein may not be used, disclosed, or published without the written consent of Biogen MA Inc.

- Type of delivery (vaginal delivery: spontaneous, induced, instrumentally supported; Caesarean section: elective, medically indicated), complications during delivery or reasons for an intervention
- Placenta normal/abnormal
- Data on newborn (sex, weight, height, head circumference, Apgar 1 minute, Apgar 5 minutes, Apgar 10 minutes)

9.4.2. Prospective Data Capture

If the pregnancy report or the pregnancy outcome report is incomplete, i.e. the data above was not collected, the open questions will be addressed during a telephone interview performed by the MSSC and the new information will be entered into the MSSC database. No further assessments other than completion of the questionnaire are applicable for patients participating in the prospective study part. The patient questionnaire is completed at a single point of time during the telephone interview performed by the MSSC.

The patient questionnaire covers the following questions:

- Abnormalities diagnosed during pediatric check-ups under statutory programs as reported in the standardized German pediatric check-up booklet “Kinderuntersuchungsheft” (data on check-ups 1-8 will be collected covering the first 46-48 months of life)
- Pregnancy and family anamnesis
- Vitamin K prophylaxis
- Body weight, height, head circumference of the child as documented for check-ups 2-8.
- Lactation:
 - Exclusive breastfeeding and duration (1st week, 1 month, 2 months, 3 months, 5 months, 6 months, 7-9 months, 10-12 months, > 12 months) of breastfeeding
 - Supplemental feedings (starting month after birth)
- Other MS therapies (non-interferon beta-1a DMTs) during or after pregnancy and start relative to birth (during pregnancy, < 1 week after birth, after 1 week, after 2 weeks, after 3 weeks, after 4 weeks, after 6 weeks, after 2 months, after 3 months, after 4 months, after 5 months, after 6 months, after 7 months, after 8 months, after 9 months, after 10 months, after 1 months, after 12 months or later))
- Frequency of MS relapses in the year before pregnancy
- Time (1st trimester, 2nd trimester, 3rd trimester) and frequency of MS relapses during pregnancy

CONFIDENTIAL

The information contained herein may not be used, disclosed, or published without the written consent of Biogen MA Inc.

- Time (< 1st month, 1st – 2nd month, 3rd - 4th month, 5th - 6th month, 7th - 8th month, 9th - 10th month, 11th - 12th month, 13th - 14th month, 15th - 16th month, 17th - 18th month, > 18th months) and frequency of MS relapses after pregnancy/birth
- EDSS before, during and after pregnancy

The information collected by the MSSC will be stored in a secure database.

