
Study Design:
	
This non-interventional, voluntary PASS is designed as a single-center open-label survey.
 
Spontaneously reported safety data are available for pregnant MS patients treated with SC interferon beta therapy or an IM interferon beta therapy in the German PSP of the MSSC.
 
In addition, a prospective data collection is performed by completing a standardized paper questionnaire while interviewing MS patients who reported a “live birth” and for which a signed ICF is available.

Population:
	
All female patients treated with SC Peginterferon beta-1a therapy or IM Interferon beta-1a therapy who fulfill the inclusion criteria are eligible to participate in the study.
 
Inclusion Criteria
 
 1. Female patients of at least 18 years at time of informed consent 2. Diagnosed RRMS or CIS (CIS indication only applicable for interferon beta-1a) 3. Exposure to either SC Peginterferon beta-1a therapy or IM Interferon beta-1a therapy before or during pregnancy 4. Registered in the PSP of the MSSC and agreed in writing to the privacy policy of the registration form 5. Reported pregnancy data (pregnancy report and pregnancy outcome report) available at MSSC. Note: only pregnancy data (i.e. obtained until 15 October 2020) will be considered. 
For the prospective part of the study:
 
 6. Ability to understand the purpose of the study and provide signed and dated study-specific informed consent form (ICF) 7. Pregnancy outcome in the retrospectively collected data was a live birth

Variables:
	
 • Demographic data • SC Peginterferon beta-1a or IM Interferon beta-1a use, including treatment duration, prior to, during and after pregnancy • Concomitant medication prior to and during pregnancy • Pregnancy outcome, including gestation week and description of abnormalities of the fetus, reason for termination, diagnostics, etc. • Complications during pregnancy • Type of delivery, complications during delivery or reasons for an intervention • Placenta normal/abnormal

CONFIDENTIAL

The information contained herein may not be used, disclosed, or published without the written consent of Biogen MA Inc.

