9.6. Data Management

MS Service-Center database:

The Biogen MS Service-Center provides medical information to German MS patients on request. Furthermore, it offers enrollment to a patient support program for SC Peginterferon beta-1a and IM Interferon beta-1a patients including injection handling training and individual adherence coaching from a personal coach upon medical need. Services have been provided since October 2014 from Audimedes GmbH, certified according to ISO 9001:2015 criteria. Compliance with these criteria is audited annually by an external certified audit organization. Database includes data of about 45,000 patients with MS.

From 2014 until December 2019 3, 615 patients under IM Interferon beta-1a treatment and 7,529 patients under SC Peginterferon beta-1a treatment have been enrolled to the patient support program. In the database, demographics and therapeutic history including adverse events, product complaints and pregnancy reports are captured in real time. All personnel dealing with the patient information and database undergo regular training to ensure quality of information, communication skills and quality of data in the database. All data is pseudonymized and pooled for this analysis.

Study database:

Data collection for the retrospective study part will be performed by extracting the relevant data from the existing MSSC database and importing it into an electronic PDF (ePDF) by a CRO. During the telephone interview, missing data will be completed directly in the ePDF, if appropriate. After the CRO has received all completed ePDFs, all

CONFIDENTIAL

The information contained herein may not be used, disclosed, or published without the written consent of
Biogen MA Inc.

data will be exported and used for analysis by the CRO as well as for updating the MSSC database (Audimedex GmbH).

All relevant data for the prospective study part is documented on standardized patient questionnaires provided as ePDF. The MSSC personnel documents the results of the telephone interview directly in the ePDF and after completion, the ePDF is transferred to the CRO to export and analyze the data together with the retrospective data.

Personal data of patients are gathered, stored and processed exclusively in a pseudonymous form according to national data protection laws.

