11.3. Monitoring and Recording Events

11.3.1. Non-Serious and Serious Adverse Events

Any pregnancies and any AEs related to the pregnancies that are analysed as part of this study have been collected and reported to Biogen in the frame of routine pharmacovigilance activities in the past. Non-serious (NSAEs) and serious (SAE) events related to study endpoints about child development and maternal MS relapses (Refer to Section 9.1 for details) will be collected prospectively from the participants in a phone interview by the MSSC and recorded as part of this study. The interview follows a predetermined structure with standardized questions. In addition, the interview may generate updates to the previously provided pregnancy data. This data will be recorded and submitted within the study.

Any other safety events (i.e. AE, pregnancies, medication errors etc.) reported spontaneously by the participants by phone will not be documented as an event within this study but will be documented and reported as spontaneous events according to standard local postmarketing channels. **Deaths**

Death is an outcome of an event. The event that resulted in death should be recorded and reported as an SAE. Biogen or designee will make every effort to obtain death certificates and autopsy reports from the reporter. The term death is reported as an SAE only if the cause of death is not known and cannot be determined.

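### Interview data can complete or update primary-endpoint items only for consenting live-birth mothers, and the protocol neither separates those data nor reconciles them with its cut-off date

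*Protocol*

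**What the plan says.** Section 9.4.1 lists what is extracted from the MSSC database. The list includes "Pregnancy outcome (live birth without defect, live birth with defects, ectopic pregnancy" and the remaining outcome categories, with gestation week and a description of fetal abnormalities. These are the variables behind the primary endpoint in 9.1.1.

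Section 9.4.2 then provides for gaps: "If the pregnancy report or the pregnancy outcome report is incomplete, i.e. the data above was not collected", in which case "the open questions will be addressed during a telephone interview performed by the MSSC and the new information will be entered" in that database. Section 9.6 describes the same step in the study file: "During the telephone interview, missing data will be completed directly in the ePDF, if appropriate". It adds that after the interview "the ePDF is transferred to the CRO to export and analyze the data together with the retrospective data". Section 11.3.1 goes a little further and says that "the interview may generate updates to the previously provided pregnancy data", to be recorded within the study.

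Interviews require a live-birth outcome and a signed consent form (9.2.1, 9.2.3.1). The primary analysis set in 9.7.1.1 is every eligible patient of the support program, interviewed or not.

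On timing, the abstract states that "only pregnancy data (i.e. obtained until 15 October 2020) will be considered", and 9.5 gives the same date as the cut-off. The same criterion in 9.2.1 gives 15 October 2021. Section 6 places prospective collection between December 2020 and 31 March 2021.

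**The concern.** The primary endpoint is a set of proportions over the whole retrospective cohort. If some records are completed or revised by a later telephone call and others cannot be, the quality of outcome information differs between records according to whether the mother responded.

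Two components are exposed. Preterm birth depends on gestation week. Live birth with or without a congenital anomaly depends on when anyone last asked. The outcome report is completed once the pregnancy has ended. The interview may come years later: services date from October 2014 (9.6) and calls run to March 2021. The same call also asks about check-up findings up to 46–48 months. With no diagnosis window in 9.1.1, nothing prevents a later diagnosis from being entered as the missing or updated anomaly status.

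The missing-data rule in 9.7 adds to this. Missing values stay in the denominator, so each completed item moves a pregnancy from the missing row into an outcome category, and this can happen only among responders. A reader could not tell how much of a reported proportion came from the reports and how much from the interviews.

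**Working it through.** **Inputs (Protocol 9.5).** There are 202 pregnancies under SC peginterferon and 245 under IM interferon. Live births number 368. The expected return is 80%, given as about 290 questionnaires.

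**Plan's own figure.** 0.80 × 368 = 294.4, which agrees with about 290. The abstract's figure of about 310 would be 310/368 = 84.2% and does not follow from an 80% return.

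**Who can be changed by interview.**
- All pregnancies: 202 + 245 = 447.
- Share of live births: 290/368 = 78.8%.
- Share of all pregnancies: 290/447 = 64.9%.

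**Who cannot be changed.**
- Live births without interview: 368 − 290 = 78 (21.2% of live births).
- Other outcomes: 447 − 368 = 79.
- Together: 78 + 79 = 157, or 157/447 = 35.1%.

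With the abstract's 310, the reachable share would be 84.2% of live births and 310/447 = 69.4% of pregnancies, so the picture is the same.

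**Effect per record.** If k pregnancies change category because of the interview, the affected proportion moves by k/447 on the default denominator of 9.7, or k/368 among live births. One record is 1/447 = 0.22 percentage points, or 1/368 = 0.27. The documents do not give k: they state neither how many reports are incomplete on anomaly status or gestation week, nor how many would be updated. The total effect therefore cannot be computed, and k = 0 is possible.

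**Dates side by side.**

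| Item | Date | Place |
|---|---|---|
| Pregnancy-data cut-off | 15 October 2020 | Abstract, 9.5 |
| Pregnancy-data cut-off | 15 October 2021 | 9.2.1 |
| Interviews | December 2020 to 31 March 2021 | Section 6 |
| Final report | 30 June 2021 | Section 6 |

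Under the 2020 date, all pregnancy data gained at interview fall after the cut-off, yet 9.6 sends them to analysis. Under the 2021 date they fall before it, but that date is later than both the end of data collection and the final report.

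**The case against.** The strongest reply is that 9.4.2 and 9.6 describe only the filling of blanks. A recorded live birth is already an entry condition for the interview, and the outcome field is coded with or without defects. For most interviewees anomaly status should therefore be present before the call, and the blanks may be items such as Apgar scores. This stands as a limit on size. A reader might infer that interview answers replace recorded outcomes throughout, but the documents do not support that. Only 11.3.1 speaks of updates, as a possibility and in the safety-recording section.

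Second, abnormalities from check-ups 1–8 are a separate secondary endpoint with its own analysis set (9.1.2, 9.7.1.2), and no section says that they reclassify the primary outcome. This also stands. Mixing of early and late anomaly diagnoses is a possibility left open, not something the plan prescribes.

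Third, a reader might try to size the effect by treating the 1.8% and the 2.1–4.1% in 7.1.2 as anomaly frequencies before and after longer follow-up. They are an interferon registry and the general population. The protocol does not attribute the difference to time since birth, and not every interviewed child would be re-ascertained.

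Fourth, the cut-off note belongs to an inclusion criterion and may select eligible pregnancies rather than freeze their data. That reading is possible, but the wording does not settle it and the two years still disagree.

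Finally, source rules often belong in the SAP. Here, however, the data flow is fixed in the protocol. Section 9.7 requires the SAP only before overall data collection ends, possibly after most calls. If values are not kept apart from the first interview, a later SAP may be unable to separate them.

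**Conclusion.** The point holds as a weakness in the written data flow. Items that determine the primary endpoint can be completed, and possibly updated, for at most about 79% of live births and 65% of pregnancies, selected by live birth, consent and contact. The completed file is what is analyzed, and no source separation is described. These shares rest on the mid-July 2020 counts and the 80% return rate in 9.5.

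Ascertainment of the primary endpoint can therefore depend on response. How far it does so cannot be derived from the protocol and may be small if few reports are incomplete. The cut-off dates contradict each other, and the 2020 date also conflicts with using interview-derived pregnancy data. The correction is worth making before interviews start, because it is cheap then and may not be recoverable afterwards.

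**What to change.** 1. In 9.4.2 and 9.6, keep interview-derived pregnancy and outcome values in separate fields of the ePDF, each with a source flag, from the first interview. The extracted report value stays alongside.
2. In 9.7.1.1, tabulate the primary endpoint on the MSSC pregnancy and outcome reports as extracted at the cut-off.
3. Add a second table with the interview-completed or updated version, in which the anomaly proportion is restricted to interviewed live births.
4. Reconcile the cut-off date across the abstract, 9.2.1 and 9.5, and state whether it selects pregnancies, freezes their data, or both.

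The cost is a source flag and separate fields in the export, and one extra table. The primary table will have somewhat more missing items. Because 9.7 keeps missing values in the denominator, category percentages there will be correspondingly lower wherever an interview would have filled a gap. The second table shows by how much.

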9.1.2. Secondary Endpoints

- Average weight, average length, and average head circumference of the children from birth to 48 months
- Number and proportion of abnormalities diagnosed during pediatric check-ups under statutory programs in Germany and reported in the standardized German pediatric check-up booklet “Kinderuntersuchungsheft” (data on check-ups 1-8 will be collected covering the first 46 - 48 months of life). Refer to Annex 3 for recommended timepoints and details on the examinations.
- Number and proportion of women discontinuing SC Peginterferon beta-1a or IM Interferon beta-1a therapy during pregnancy and time to discontinuation in relation to beginning of pregnancy

CONFIDENTIAL

The information contained herein may not be used, disclosed, or published without the written consent of Biogen MA Inc.

- Number and proportion of women starting SC Peginterferon beta-1a or IM Interferon beta-1a therapy during pregnancy and time to start in relation to beginning of pregnancy
- Number and proportion of women restarting SC Peginterferon beta-1a or IM Interferon beta-1a therapy after birth and time to restart in relation to birth
- Number and proportion of women starting another MS therapy during/after pregnancy and time to start in relation to birth
- Number and proportion of women using other therapies during pregnancy (categorized by Paracetamol, other therapies for the alleviation of FLS), folic acid, medication for depression, corticosteroids, adrenocorticotrophic hormone, other therapies)
- Number and proportion of MS relapses in women with SC Peginterferon beta-1a or IM Interferon beta-1a therapy before, during and after pregnancy
- Change of EDSS during and after pregnancy to EDSS before pregnancy
- Lactation: number of women breastfeeding under SC Peginterferon beta-1a or IM Interferon beta-1a therapy and duration of SC Peginterferon beta-1a or IM Interferon beta-1a exposed breastfeeding
- Time to first MS relapse after introduction of the first supplemental feedings in women with SC Peginterferon beta-1a or IM Interferon beta-1a therapy during lactation

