9.7.2. Subgroup Analysis

Subgroup analyses will be performed with respect to patient's interferon beta-1a treatment history before during and after pregnancy. The primary endpoint will be evaluated in following subgroups:

- SC Peginterferon beta-1a or IM Interferon beta-1a was taken continuously before and during pregnancy
- SC Peginterferon beta-1a or IM Interferon beta-1a therapy was paused/stopped during pregnancy
- SC Peginterferon beta-1a or IM Interferon beta-1a therapy was started during pregnancy

The secondary endpoints will be evaluated in following subgroups:

- SC Peginterferon beta-1a or IM Interferon beta-1a was taken continuously before, during and after the pregnancy
- SC Peginterferon beta-1a or IM Interferon beta-1a therapy was started during pregnancy
- SC Peginterferon beta-1a or IM Interferon beta-1a therapy was paused during pregnancy and restarted promptly (within 1 week) after "life birth"
- SC Peginterferon beta-1a or IM Interferon beta-1a therapy was stopped during pregnancy and restarted more than a week after "life birth"
- SC Peginterferon beta-1a or IM Interferon beta-1a therapy was stopped during pregnancy and not restarted after "life birth"

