9.8. Quality Control

The study will be conducted and reported in accordance with the “Guideline on good pharmacovigilance practices (GVP) Module VIII - Post-authorisation safety studies”.

Data management and quality assurance for the study are in accordance with the German document „Gemeinsame Bekanntmachung des Bundesinstituts für Arzneimittel und Medizinprodukte (BfArM) und des Paul-Ehrlich-Instituts (PEI) zur Anzeige von Anwendungsbeobachtungen nach §67 Absatz 6 Arzneimittelgesetz und zur Anzeige von nichtinterventionellen Unbedenklichkeitsprüfungen nach §63f und g Arzneimittelgesetz“ in the final version of December 20th, 2019.

Retrospective data are automatically checked for plausibility, completeness and mandatory information by programmed edit checks during the data entry by the MSSC in their database. Pregnancy data is further checked for consistency and plausibility by a trained medical documentation officer before being sent to Biogen Pharmacovigilance department. By using the ePDF for the patient questionnaire, data are entered by the MSSC in a standardized way and simple checks are implemented. The prospective and retrospective data of lactation and Interferon therapy will be manually cross-checked for consistency by MSSC.

MSSC checks also the patient questionnaires (ePDF) manually for potential adverse and other safety events and reports the events to the Sponsors Pharmacovigilance as per section 11.3.

For quality control purposes, random samples of all MSSC contacts are checked for compliance with Good Documentation Practice and missed adverse events on a daily basis. Pharmacovigilance relevant information is further checked for consistency and integrity by a trained medical documentation officer and is submitted directly to Biogen or to appointed third parties for pharmacovigilance services.

Due to the non-interventional character of the study, missing values and/or implausibility may persist and will be accepted.

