16. ANNEX 3: ADDITIONAL INFORMATION

Flowchart

	MSSC database	Patient questionnaire
Prior to enrollment (i.e. generating data extract for pregnancy reporting data from MSSC database and obtaining written informed consent for prospective study part)		
Selecting eligible participants by checking Inclusion/Exclusion Criteria	X	X
Ensuring that written agreement on the privacy policy of the PSP registration form is available	X	---
Identification of missing data in MSSC database	X	---
Contacting eligible participants by phone, explaining background of the proposed study, the data collected, and the voluntary nature of study participation, obtaining oral consent for proceeding with the prospective study part	---	X
Provision of Patient Information and collection of written Informed Consent	---	X
After enrollment		
Date of Informed Consent	---	X
Patient's demographics: age, weight, height	X	---
Pregnancy outcome, type of delivery, complications	X	---
Pregnancy anamnesis	---	X
Data on the newborn child	X	X
Family anamnesis of child	---	X
Data on child development (as reported in the standardized German pediatric check-up booklet "Kinderuntersuchungsheft")	---	X
Breastfeeding practices	---	X
Interferon beta treatment history before, during and after pregnancy	X	---
Other MS medications during and after pregnancy	---	X
Concomitant medication during and after pregnancy	X	---
MS disease activity	---	X
Premature Study Termination (only applicable for prospective study part)	X	---

CONFIDENTIAL

The information contained herein may not be used, disclosed, or published without the written consent of Biogen MA Inc.

Health checks for children in Germany as reported in the standardized German pediatric check-up booklet “Kinderuntersuchungsheft”

Examination type	Age	Scope of examination
U1	After birth	Skin colour, breathing, muscle tone, reflexes, heartbeat, Vitamin K prophylaxis
Advanced newborn screening	1–3 days old	Blood test to check for metabolic disorders
Newborn hearing screening	1–3 days old	Exclusion of hearing impairments from a hearing loss of 35 dB
Cystic fibrosis screening	1–3 days old	Generally a blood sample taken during advanced newborn screening
Pulse oximetry screening	2 days old, by U2 at the latest	Measurement of the blood oxygen levels using a light sensor on the baby’s foot. Low oxygen levels can be a sign of congenital heart defects. Vitamin K prophylaxis

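### Interferon restart after birth has no standing interview item, so a restart after the last database entry can be missed without showing as missing

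*Protocol*

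**What the plan says.** **What is to be estimated.** Protocol 8.1 names as an aim whether and when interferon is continued postpartum. Section 9.1.2 lists "Number and proportion of women restarting SC Peginterferon beta-1a or IM Interferon beta-1a therapy after birth and time to restart in relation to birth", the number of women breastfeeding under interferon with the duration of exposed breastfeeding, and time to first relapse after supplemental feeding begins in women treated during lactation. Section 9.7.2 splits the secondary subgroups by post-birth status: continued throughout, restarted within a week, restarted later, or not restarted. No time horizon is given for the last.

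**Where the data come from.**
- Section 9.4.1 lists interferon use before, during and after pregnancy as a database extract. It describes the main source as the pregnancy report and the "pregnancy outcomes report (to be completed after completion of pregnancy").
- Section 9.4.2 lists the questionnaire's treatment item as "Other MS therapies (non-interferon beta-1a DMTs) during or after pregnancy and start relative to birth". Report items that were not collected are to be asked in the interview.
- The Annex 3 flowchart marks "Interferon beta treatment history before, during and after pregnancy" for the database and not for the questionnaire. Section 9.3 points to this annex for what is collected.
- The comment to Section 5 of the Annex 2 checklist says that drug exposure is collected retrospectively only.
- Section 9.8 says: "The prospective and retrospective data of lactation and Interferon therapy will be manually cross-checked for consistency by MSSC".

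**The concern.** The study drug is the one post-birth treatment with no listed question in the interview. The other time-dependent items run well past delivery in Section 9.4.2: relapses beyond 18 months, breastfeeding beyond 12 months, and other MS therapies to 12 months or later. Interferon status runs only to the last database entry, and the protocol does not say when that is.

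If a woman restarts after that entry, her record can still show no restart. She could then be tabulated as 'not restarted', her time to restart would be lost, and relapses on resumed treatment would be described in a subgroup that appears to be off treatment. Exposed breastfeeding could be undercounted in the same way. The questionnaire is completed once and participation ends with it (Section 9.2.3.1), so the information cannot be recovered later within the study.

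**Working it through.** **Step 1: the plan's own figure.** Section 9.5 gives 368 live-birth pregnancies and an 80% return rate: 368 × 0.80 = 294.4, consistent with the stated figure of about 290 questionnaires. These are pregnancies, not women: 202 + 245 = 447 reports come from 184 + 199 = 383 patients.

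**Step 2: what happens to each kind of record.**

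| Post-birth interferon in the database | Asked in interview? | Appears as |
|---|---|---|
| Blank | Yes, as an uncollected item (9.4.2, 9.6) | Answered, or 'Missing' (9.7) |
| Restart recorded | Not required | Restart |
| No restart recorded, still true at interview | Not required | Correct |
| No restart recorded, restart came later | Not required | Looks complete; out of date |

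The last row is the gap. The interview fallback and the 'Missing' row both act on blanks, and this record is not blank.

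**Step 3: can the Section 9.8 cross-check catch it?** By the flowchart, interferon history is in the database only and breastfeeding practices are in the questionnaire only. Neither topic has a standing entry in both sources. Read literally, the cross-check needs prospective interferon data that Sections 9.4.2, Annex 2 and Annex 3 do not provide for. Read as questionnaire lactation against database interferon, it can expose some inconsistencies but not a restart that neither source holds.

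**Step 4: how large could it be?** The protocol gives no restart rate and no report timing, so this is an illustration only. Let N = 290 questionnaires, r = the assumed true share restarting more than a week after birth, and m = the assumed fraction of those restarts not on record and read as no restart.

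- Records moved = N × r × m
- Observed late-restart share = r × (1 − m)

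| r | m | Moved | Observed share |
|---|---|---|---|
| any | 0 | 0 | r |
| 30% | 25% | 290 × 0.30 × 0.25 = 21.75 | 22.5% |
| 30% | 50% | 290 × 0.30 × 0.50 = 43.5 | 15% |
| 50% | 25% | 290 × 0.50 × 0.25 = 36.25 | 37.5% |
| 50% | 50% | 290 × 0.50 × 0.50 = 72.5 | 25% |
| 70% | 25% | 290 × 0.70 × 0.25 = 50.75 | 52.5% |
| 70% | 50% | 290 × 0.70 × 0.50 = 101.5 | 35% |

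The range is 0 to about 102. Because r is a share of all questionnaires, it falls as more women continue treatment throughout and have no restart to miss.

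**The case against.** A reader might infer that restart is taken only from reports that close at delivery, that the interview never asks about it, that late restarters are filed as not restarted, and that the results are therefore wrong. The protocol does not support that reading:

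- The outcome report is due after the pregnancy ends, with no closing date. Section 9.6 adds that therapeutic history is captured in the database in real time, so later restarts may be on record.
- Blank items are asked by telephone, and interferon use after pregnancy is among the items covered.
- No rule classes an unrecorded restart as 'not restarted'. Section 9.7 shows missing data as such and imputes nothing. How subgroups are derived is ordinary SAP content, and the SAP is not shown.
- The full questionnaire is not among the documents, and Section 9.8 may imply that some interferon data are obtained in the interview.

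The consequences are also bounded. The primary endpoints and primary subgroups need no post-birth interferon data, and the child-development objective concerns exposure before and during pregnancy. Restart within a week is the subgroup least exposed to missed late restarts. All affected outputs are secondary and descriptive.

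These points rule out calling this an established error. They do not close the gap in Step 2. Real-time capture holds only what reaches the center, and no section requires a contact after the outcome report or gives a date to which the history is complete. The SAP cannot restore data that were never asked for.

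**Conclusion.** The point holds as a gap in data capture and an inconsistency between Sections 9.4.1, 9.4.2 and 9.8, Annex 2 and Annex 3. A restart after the last database entry can go unseen without counting as missing. This can bias the restart proportion, time to restart, breastfeeding under interferon, and above all the division between late restart and no restart.

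The direction is towards too few restarts, provided that an outdated entry is read as no restart. The size cannot be determined from the protocol. The illustrative range rests wholly on assumed values of r and m, and it is zero if database histories are current or if doubtful cases are reported as unknown. The correction is worth making before the first interview because it is cheap then and impossible within the study afterwards.

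**What to change.** 1. Add one standing questionnaire item for every interviewed woman, whether or not the report looks complete: interferon restarted after birth (yes/no), product, month of restart, and month of any later stop up to the interview.
2. Mark the questionnaire column for interferon history in the Annex 3 flowchart, and reconcile Sections 9.4.1, 9.4.2 and 9.8 and the Annex 2 comment with it.
3. Derive the post-birth endpoints and the Section 9.7.2 secondary subgroups from the interview item, and use the database value for the Section 9.8 cross-check, which then has two sources to compare.
4. Report restart status as unknown where neither source covers the period.

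The cost is one question in a call already planned, plus changes to the ePDF and protocol wording before interviewing starts. The downside is that restart dates would be recalled, as relapse and feeding dates already are.
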